# Safety:

Adverse events, serious adverse events (SAEs), and medical device incidents will be monitored and reported throughout the entire course of the study. The AE reporting period begins when the patient is consented to participation in the study (date of informed consent signature) and continues through the study discontinuation date. Adverse events ongoing at study discontinuation will be followed up until resolution or stabilisation.

Kimberly-Clark
Version 3.0 dated 28 Jan 2022
Clinical Investigation Plan No. KCC-DN-001
Page 14 of 71

# **Data Management:**

Investigators and site personnel will enter the data required by the clinical investigation plan using a fully validated and 21 CFR Part 11-compliant electronic data capture (EDC) system. All participating sites will have access to the entered data regarding the individual site of its own enrolled patients. For electronic patient-reported outcomes (ePROs), the data entered by the parents/carers will be directly captured into the EDC.

Full Study Title : Effect of use of DryNites® absorbent pants on the rate of spontaneous resolution of paediatric nocturnal enuresis (NE)					
Phase:	Phase:Phase IVType:Clinical Investigation				
Number of Patients: 120			n of Patient Participation:  (primary endpoint) – optional extension		
Number of Sites: 7-12			n of Study: 3 years		

#### **Statistical Considerations:**

The analysis sets will be the following: Screened Set (all patients enrolled), Randomised Set, Primary Analysis Set (all patients randomised without major violation of the clinical investigation plan), Extension Set.

Demographic and baseline characteristics, disease history, physical examination and medical history will be summarised with appropriate descriptive statistics by group and separately for age subgroups on Screened and Randomised Sets.

The Absorbent Pants Clinical Trial Questionnaire administered at study entry, and the DryNites® Clinical Trial Questionnaire administered at the end of the run-in period, will be analysed descriptively for the Screened Set.

Direct-to-patient data will be analysed descriptively at each assessment along with applicable change from baseline on Randomised and Primary Analysis Sets.

The primary outcome (i.e., average number of wet nights in Week 4 of the core study period) will be analysed on the Primary Analysis Set comparing the 95% confidence interval (CI) for the difference between the means of the 2 groups with the predefined margin ( $\delta = 2/7$ ). If the CI lies strictly within [- $\delta$ , + $\delta$ ], the study hypothesis will be demonstrated. The primary outcome will be then presented by age group (4–<6 years,  $\geq$ 6–8 years).

Secondary outcome will be presented by group on Randomised Set. Frequency distribution and descriptive statistics, when applicable, will be provided by visit for each item of questionnaires, while summary statistics for total scores, domain scores and changes from baseline will be provided as applicable for the PinQ, the WHOQoL-BREF, PDSS and CIS. The effect size will also be presented as descriptive statistics of ratio between the change from baseline and baseline standard deviation (SD). The percentage of patients with change from baseline ≥0.5 time the SD will also be provided. For applicable questionnaires, a covariance analysis model (ANCOVA) with baseline PROs value as covariate will be performed. Group comparisons will be performed for the difference in least squares means (LSMean) at Day 56±7 days. The same analysis will be repeated using a repeated measure model to assess the extension period effects.

Full Study Title: Effect of use of DryNites® absorbent pants on the rate of spontaneous resolution of					
paediatric nocturnal enuresis (NE)					
Phase:	Phase:   Phase IV     Type:   Clinical Investigation				
Number of Patients: 120		Duration of Patient Participation :			
		8 weeks (primary endpoint) – optional extension			
		of 4 weeks			
Number of Sites: 7-12		Duration	of Study: 3 years		

For each group, numbers and proportion of treatment-emergent adverse events (TEAEs), device-related TEAEs, serious TEAEs and medical device incidents will be tabulated by preferred term and system organ class. All safety analyses will be performed on the Safety Analysis Set. All the events occurred from ICF signature till randomisation will be described separately.

#### Sample size

The statistical hypothesis behind the present study design is the equivalence in rate of spontaneous resolution of NE at  $56 \pm 7$  days between discontinuing and continuing nocturnal use of DryNites® absorbent pyjama pants in children with NE. The margin for non-inferiority is set to 2/7 wet nights with an expected proportion of 0.95 and 0.80 wet nights, respectively for continuing and discontinuing use of absorbent pants group. The power is set to 99%.

Fifteen participants are needed in the continuation arm to obtain a power of 99%. This means that a total of 45 participants are needed at randomisation (due to the 2:1 randomisation). Fifteen additional participants are added to this number (total of 60 participants) to compensate for dropouts/poor compliance during the trial, and for the participants who will be excluded at randomisation because they did not fulfil the criteria of 7 wet nights per week. Additionally, the primary endpoint will be analysed separately for the 2 age groups (4–<6 and  $\geq$ 6–8 years of age) and therefore 60 participants will be needed for each age group (total 120 participants).

As such, 120 participants should be recruited, with approximately half of the participants should be in the younger age group, age 4-<6 years, and half of the participants should be in the older age group,  $\ge 6-8$  years.

#### **Interim and Final Analyses:**

No interim analyses are planned. The primary and secondary analysis will be performed after the completion of 4 weeks post randomisation phase. Applicable analyses will be repeated at the end of the extension period.

Full Study Title : Effect of use of DryNites® absorbent pants on the rate of spontaneous resolution of paediatric nocturnal enuresis (NE)					
Phase:	Phase:   Phase IV     Type:   Clinical Investigation				
Number of Patients: 120			eks (primary endpoint) – optional extension weeks		
Number	of Sites: 7-12	Durat	ation of Study: 3 years		

# **Ethical and Regulatory Considerations:**

This clinical investigation will be conducted in accordance with the clinical investigation plan and all applicable laws and regulations including, but not limited to Good Clinical Practices (GCP), International Organization for Standardization (ISO) 14155, the Directive 93/42/EEC and Regulation 2017/45/EU, as applicable, and the ethical principles that have their origins in the Declaration of Helsinki and applicable privacy laws. Data protection and privacy regulations will be strictly observed in capturing, forwarding, processing, and storing patient data. Every effort will be made to protect participant confidentiality according to the General Data Protection Regulation (EU) 2016/67. An Institutional Review Board (IRB)/ Independent Ethics Committee (IEC) must review and approve the clinical investigation plan, ICF and paediatric assent form (where applicable by local regulations) before any patients are enrolled. The parents/legally authorised representatives of the patient must sign and date the IRB/IEC-approved informed consent form before any clinical investigation plan-directed data collection is performed.

# **Documentation of Amendments to the Clinical Investigation Plan**

Amendment #2: 28 January 2022

Sections modified and updates	Reason
4.1 Study design	Text has been updated to reflect the optional use of
All participants will receive absorbent bed mats to	bed mats.
use every night, however, the use of bed mats is	
optional.	
4.3 Study population	Extension of study recruitment from 15 to 30
The study will aim to randomise approximately	months due to low recruitment during the Covid-19
120 participants aged 4-8 years from a total of 7-	pandemic period.
12 sites in 3 countries (Belgium, Denmark, and	
the United Kingdom) over a 30-month enrolment	
period.	
4.3.8 Clinical investigation plan deviations	The number of individual violations required to
The following events will be considered as	define a major violation and exclude the data from
the major violations of the clinical	the analysis has been relaxed to "up to 4" instead of
investigation plan and lead to the exclusion	"\geq 3 violations".
of the participant's data from the analysis:	
Absorbent pants/nappies (of any)	
brand) used nocturnally in the 'no	
pants' group (up to 4 violations of	
the clinical investigational plan	
over the 4-week trial period will	
merit exclusion; these will be	
documented in the diary)	
No pants, or absorbent pants of a	
different brand, used nocturnally in	
the DryNites® group (up to 4	
violations of the clinical	
investigation plan over the 4-week	
trial period will merit exclusion;	
these will be documented in the	
diary)	

 
Initiation of a prescribed therapy for NE
 
	
(pharmacologic or bed alarm)	
4.4.2 Provision of Study Treatment	Text has been updated to reflect the optional use of
Study treatment and absorbent bed mats will be	bed mats.
supplied to the participants by the	occ mais.
Investigator/site; however, the use of bed mats is	
optional.	
4.5.3.2 Physical examination	Text has been updated to reflect that baseline visits
The baseline visit can be performed remotely.	can be performed remotely as well. In case of a
In case a remote baseline visit is performed,	remote visit, the Investigator must check the
height/weight and full physical examination will	subject's history of verified urinary tract infections,
not be recorded. In this scenario, the Investigator	congenital abnormalities of the urinary tract, and
must check the medical records and/or interview	surgery on the urinary tract to determine eligibility.
the parent/carer to investigate history of	surgery on the armary tract to determine engionity.
congenital abnormalities of the urinary tract,	
history of surgery on the urinary tract, and history	
of verified urinary tract infections before	
determining eligibility.	
uctermining engionity.	

Footnote text has been updated to reflect that the baseline visit can be performed remotely when an

height/weight record and physical examination in

on--site visit is not possible and add clarity on

case of a remote visit

Table 2 Schedule of assessments Table footnotes:

- (a): Baseline visit can be performed remotely.
- (b): In case a remote visit was performed, height/weight will not be recorded.
- (c): In case a remote visit was performed, a full physical examination will not be recorded. In this scenario, the Investigator must check the medical history and/or interview the parent/carer to investigate history of congenital abnormalities of the urinary tract, history of surgery on the urinary tract, and history of verified urinary tract infections
- (d): AEs, SAEs and Medical Device Incidents are collected from ICF signature onwards.
- (e): Review of diary data by the Investigator/treating physician.
- (f): For participants who meet the randomisation criterion.
- (g): For all participants at the end of the run-in period.

Text has been updated to reflect that the baseline visit can be performed remotely and add clarity on how height/weight and the physical examination will be recorded in case of a remote visit.

- 4.7.1 Visit 1 baseline visit
  Baseline visit can be performed remotely.
  \*In case a remote visit was performed,
  height/weight will not be recorded.

  \*\*In case a remote visit was performed a
- \*\*In case a remote visit was performed, a full physical examination will not be performed. The Investigator must check history of congenital abnormalities of the urinary tract, history of surgery on the urinary tract, and history of verified urinary tract infections.

Additional minor changes have been made to maintain consistency of the document.

# **Milestones**

Milestone	Timelines
Final clinical investigation plan	11 Sep 2019
First patient in	21 Feb 2020
Last patient out	Q4 2022
Final report of study results	Q2 2023

Abbreviations: Q: quarter.

# 1 INTRODUCTION

# 1.1. Background

Nocturnal enuresis (NE) is a stressful occurrence for both children and their families, which can have negative emotional and social implications for sufferers (NICE 2014, NICE 2010). It can significantly reduce the child's self-esteem, increase the likelihood of behavioural problems, and impact their attachment style (Coppola et al. 2011). It can also lead to increase

in parental anxiety and depression (Tanriverdi et al. 2014, Meydan et al. 2012).

In addition, NE can lead to poor quality, interrupted sleep for both sufferers and their families (NICE 2014, NICE 2010, Ertan et al. 2009). To add to this, the burden of bed-wetting is frustrating and costly to families (NICE 2014, Paediatric Society of New Zealand 2005). As children in Europe often begin school at age 4–5 years, many families become interested in resolving enuresis at this age.

Absorbent pants may reduce the impact of NE on the quality of life (QoL) of both children and their families, through reducing the burden and cost of wet beds, and reducing night-time awakenings (Urology Care Foundation, Kushnir et al. 2013).

Guideline recommendations on the management of NE are not comprehensive, and while many treatment options are available, advice on use of absorbent pants is limited (NICE 2014, NICE 2010, Paediatric Society of New Zealand 2005, Urology Care Foundation, Nevéus et al. 2010, Feldman 2005).

Use of absorbent pants for the management of NE is a controversial area, with many groups expressing conflicting opinions on the issue. Some recommend against using absorbent pants, stating that they reduce the incentive for children to become dry and can delay attainment of dryness (Uptodate, Nocturnal enuresis, Fleming 2012). Even though undocumented, in many countries (e.g., China, Sweden, and Germany) health care professionals (HCPs) recommend against using absorbent pants to manage NE.

#### 1.2. Rationale

No evidence is available to suggest that the use of absorbent pants slows resolution of NE, or that removal of absorbent pants improves resolution of NE.

Furthermore, there are currently no evidence-based recommendations supporting the use of absorbent pants for management of NE, and the lack of clear guidance supporting the benefits

of using absorbent pants may have resulted in many children and their families not benefitting from this possible solution.

As such, this study aims to demonstrate that continuing nocturnal use of absorbent pants in children with NE does not have a negative impact on the rate of spontaneous resolution of NE, compared with discontinuing use of absorbent pants. It also aims to show that use of absorbent pants may provide additional QoL and sleep benefits for both children and their parents/carers. The age group 4–8 years is recommended for inclusion in this study, as this will involve families who become interested in resolving enuresis before or shortly after starting school. Age 8 years was chosen as the cut-off, as by this age many children who continue to experience NE will have been exposed to treatment of some sort.

Nocturnal Enuresis can vary in severity from 1 night per week to every night per week. This study will evaluate children with severe NE, who usually experience NE every night of the week. Although the rate of spontaneous resolution is low in this group, it is the most appropriate and reliable population to study. Children who experience NE for <7 nights per week are a heterogeneous group whose rate of NE may vary weekly; as such, many confounding variables could affect the trial results if this population was used.

# 1.3. Lay Summary

Bed-wetting is stressful for both children and their parents/carers. In almost all cases, children will stop bed-wetting without any need for treatment. Children vary in the age at which they achieve night-time dryness. Regardless of whether or not a parent/carer chooses to use a medical treatment to help speed up achievement of night-time dryness (e.g., use of an alarm or medication), night-time use of absorbent pants can help to reduce the burden of wet beds until the child is completely dry every night. Some experts believe that the use of absorbent pants can prevent the child from learning night-time bladder control, while others believe it has no impact on the rate at which children become dry. This study aims to show that using DryNites® absorbent pants does not have a negative effect on the speed that children become dry, compared with removing absorbent pants. It also aims to show that using DryNites® improves the overall quality of life and sleep quality of both children and their parents/carers.

# 2 BENEFIT/RISK AND ETHICAL ASSESSMENT

DryNites® pyjama pants are absorbent pants designed to reduce the burden of bed-wetting, commercially available since 1995. DryNites® are registered as class I medical devices and CE marked. They are not a treatment for NE and are not designed to cure NE.

The side-effects of using DryNites® have not been evaluated in any studies. Minor side-effects may include sweating or rash (Cohen 2017). No severe side-effects are anticipated.

All trial participants will use DryNites® for the 4-week run-in period at the start of the trial. Following this, participants will be randomised to discontinue or continue use of DryNites® in a 2:1 ratio for another period of 4 weeks (the discontinuation of the use of pants being the intervention). There is no placebo comparator in this trial. Safety will be monitored at each trial visit. The parents of trial participants will be asked whether the child has experienced any side-effects or discomfort while wearing the DryNites®.

In addition, all participants will be provided with DryNites Bed Mats to be used during the study period, however, the use of bed mats is optional.

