#### 4.6. Adverse Events

The definitions, recording and reporting of an AE, SAE or Medical Device Incident can be found in Section 7.

Adverse events will be reported by the participant, parents/carers, or the participant's legally authorised representative.

The Investigator and any designees are responsible for detecting, documenting, and recording events that meet the definition of an AE or SAE and remain responsible for following-up AEs that are serious, considered related to the study treatment or study procedures, or that caused the patient to discontinue the study treatment.

Care will be taken not to introduce bias when detecting AEs and/or SAEs. Open-ended and non-leading verbal questioning of the participant is the preferred method to inquire about AE occurrences.

Documentation regarding the AE should be made as to the nature, date of onset, end date, severity, relationship to product, action(s) taken, and outcome of any sign or symptom observed by the physician or reported by the patient/parents/carers upon indirect questioning.

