# **4.6.1.** Time Period and Frequency for Collecting Adverse Event and Serious Adverse Event Information

All AEs will be collected from the date of written informed consent granted by the parent(s)/carer(s) onwards until discontinuation of the study at the time points specified in the schedule of assessments.

All SAEs will be recorded in the eCRF within 24 hours of awareness; this will trigger an immediate email notification of the SAE to the Sponsor. The Investigator will record any updated SAE data in the eCRF within 24 hours of it being available; this will trigger an email notification of the SAE follow-up report to the Sponsor accordingly.

Investigators are not obligated to actively seek AE or SAE after conclusion of the study participation. However, they will follow-up any AE ongoing at study discontinuation until resolution or stabilisation.

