#### 4.7.4. Visit 3 - End of Intervention Period/Enrolment in Extension Period Visit

The following assessments will be performed for all enrolled patients at the end of the core study period:

- Any AEs occurred or ongoing since the previous visit
- Concomitant medications for AEs
- Review of the diary data
- PROs: PinQ, WHOQOL, PDSS, CIS
- Willingness to participate in the extension period
- Complete the Disposition/End of study form for participants not willing to enrol in the extension

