#### 7 SAFETY REPORTING

All AEs, regardless of relationship to the study treatment or intervention, will be monitored and reported throughout the entire course of the study. The AE reporting period begins when the patient is consented to participation in the study (date of first signature of informed consent) and continues through the study discontinuation date. AEs will be recorded on the appropriate eCRF forms.

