16.1 Adverse Events

Adverse Events (AEs) will be coded using the version of MedDRA available at the time of the analysis.

Treatment emergent adverse events (TEAEs) are defined as AEs that first occurred or worsened in severity after the start of screening period and prior to the end of the extension period.

See Appendix 1 for handling of partial dates for AEs. In the case where it is not possible to define an AE as treatment emergent or not, the AE will be classified by the worst-case scenario; i.e. treatment emergent.

The AEs that occurred from ICF signature till randomisation will be described separately and presented in a listing.

For each group, numbers and proportion of TEAEs, device-related TEAE and serious TEAEs will be tabulated by SOC and PT along with number of events.

Medical Device Incidents (MDI) not associated with a TEAE will be described separately in a listing.

Document:	Y:\Kimberly-Clark\DryNites\Documentation\SAP\DryNites_SAP_v1.0_20200203		
Author:	[name]	Version Number:	1.0
		Version Date:	03Feb2020
Template No.: I	RWI_TP_BIOS0013 Revision 1		Reference: RWI_WI_BIOS0015

Effective Date: 15Jun2018

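### A side-effect question tied to wearing DryNites gives the DryNites arm an extra adverse-event prompt after randomisation, with no counterpart in the No Pants arm

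*Protocol*

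**What the plan says.** Two parts of the protocol describe how AEs are to be elicited.

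- Section 2 (benefit/risk) says "Safety will be monitored at each trial visit" and continues: "The parents of trial participants will be asked whether the child has experienced any side-effects or discomfort while wearing the DryNites".
- Section 4.6 (adverse events) says "Care will be taken not to introduce bias when detecting AEs and/or SAEs" and then: "Open-ended and non-leading verbal questioning of the participant is the preferred method to inquire about AE occurrences". It makes no distinction between arms.

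Collection is broad in both arms. Section 4.6.1: "All AEs will be collected from the date of written informed consent granted by the parent(s)/carer(s) onwards until discontinuation of the study". Section 7: "All AEs, regardless of relationship to the study treatment or intervention, will be monitored and reported throughout the entire course of the study". The visit lists in sections 4.7.3 to 4.7.6 each include AEs. For Visit 3 the list is introduced by "The following assessments will be performed for all enrolled patients at the end of the core study period". None of these lists mentions the DryNites question.

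Section 7.2 lists the variables recorded for each AE: verbatim term, dates, severity, seriousness, relationship to the device, action taken, outcome, and whether the event led to withdrawal. None says whether the event was volunteered, given in answer to an open question, or given in answer to a specific one.

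On reporting, SAP section 16.1 says: "For each group, numbers and proportion of TEAEs, device-related TEAE and serious TEAEs will be tabulated by SOC and PT". Protocol section 5.4.4 plans the same tabulation.

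**The concern.** During the run-in every child wears DryNites, so the question applies equally to all. From randomisation, two thirds of children stop wearing pants. A question limited to time in DryNites then has nothing to ask about in the No Pants arm, apart from deviations, but it can still bring out minor complaints in the DryNites arm. There is no equivalent question about, for example, discomfort without pants.

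The events at issue are mild and local. Section 2 names sweating and rash as possible minor side-effects and says that the side-effects of DryNites have not been evaluated in any study. Such events are sensitive to how the question is put, and the trial is open-label. Section 2 also describes stopping pants as the intervention, so a reader of the by-group TEAE table will naturally take it as a comparison of stopping with continuing. If the arms are questioned differently, part of any difference may come from the questioning. Because the form does not record the source of an event, this could not be examined afterwards.

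**Working it through.** The plan gives no AE rate or capture rate, so there is no stated figure to reproduce. The check sets the passages side by side and adds a labelled illustration.

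**What each arm is asked**

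| Visit | DryNites arm | No Pants arm |
|---|---|---|
| Visit 2 (covers run-in) | Open AE questioning + DryNites question | The same; all children wore DryNites |
| Visits 3 and 4 (cover post-randomisation time) | Open AE questioning + DryNites question, if repeated | Open AE questioning only, in effect |

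The contrast after randomisation is open questioning plus one device prompt against open questioning alone. It depends on the DryNites question being repeated at Visits 3 and 4. Section 2 places it directly after the sentence on monitoring at each visit but does not itself name a visit.

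**Which events reach the by-group tables**

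- Protocol section 5.4.4 counts TEAEs from randomisation, so only the asymmetric period enters.
- SAP sections 4.3 and 16.1 count them from the start of screening, so run-in events, elicited alike in both future arms, also enter. SAP 16.1 additionally lists pre-randomisation AEs separately.

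**Illustration of size (assumed values)**

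Let p be the true post-randomisation AE risk, equal in both arms. Let c be the share of events that open questioning captures relative to open questioning plus the prompt. The DryNites arm then shows p, the No Pants arm shows p × c, and the spurious excess is p − p × c = p(1 − c).

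| p | c = 1 | c = 0.9 | c = 0.75 | c = 0.5 |
|---|---|---|---|---|
| 10% | 0 | 1.0 point | 2.5 points | 5.0 points |
| 20% | 0 | 2.0 | 5.0 | 10.0 |
| 30% | 0 | 3.0 | 7.5 | 15.0 |

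In counts, if all 120 children were randomised 2:1 (40 DryNites, 80 No Pants), p = 10% and c = 0.75 gives 40 × 0.10 = 4 children against 80 × 0.10 × 0.75 = 6, that is 10% against 7.5%. Protocol section 5.2 counts screen failures within the 120, so the actual numbers may be smaller. The percentages do not depend on them.

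**Effect of the SAP window**

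Let r be the run-in AE risk, the same in both arms and independent of later events. The share of children with at least one TEAE is 1 − (1 − r)(1 − p) with DryNites and 1 − (1 − r)(1 − pc) without, so the excess becomes (1 − r) × p(1 − c). Assuming r = p = 10% and c = 0.5:

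- DryNites: 1 − 0.90 × 0.90 = 19.0%
- No Pants: 1 − 0.90 × 0.95 = 14.5%
- Excess: 4.5 points, against 5.0 points (10% against 5%) under the protocol window

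The absolute gap shrinks slightly. The relative gap shrinks more, because both percentages rise.

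**The case against.** The strongest reply is that both arms are actively asked about AEs at the same visits. A reader might infer that the tables set prompted reporting against unprompted reporting. The documents do not support that: section 4.6 has no arm restriction, sections 4.7.4 and 4.7.5 list AEs for all enrolled patients, and section 7 requires every AE whatever its relationship. This stands, and it limits the issue to one additional prompt.

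A reader might also infer that harm from stopping pants would be hidden. That does not follow. A skin problem from a wet bed is an AE and is reportable in either arm; the lack of a matched prompt may reduce capture but does not exclude the event.

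Section 2 is a benefit/risk narrative, and its question could be satisfied at Visit 2 alone, where it is symmetric. That reading is possible, but neither document adopts it, and the neighbouring sentence refers to each visit. Section 4.6 calls open questioning the preferred method, not the sole one, so the two passages can coexist. Even so, nothing says how they fit together.

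Finally, the SAP's safety objectives are to describe events (section 3.4), and section 8.1 plans no confirmatory testing. Relatedness to DryNites is already not applicable in the No Pants arm (protocol section 7.1.5), so device-related TEAEs are openly arm-specific. Any bias would also run against the sponsor's own product. All of this limits the consequence. It does not remove the asymmetry from the all-TEAE table, which is the one that looks comparable.

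**Conclusion.** The point holds as a minor one. If the section 2 question is asked after randomisation, the DryNites arm receives a device-specific prompt that the No Pants arm does not, and the form cannot separate the resulting events. The by-group TEAE tables are then open to differential ascertainment of mild local events, towards more events with DryNites.

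The size cannot be determined from the documents. It is zero if open questioning captures everything (c = 1) or if the question is asked only at Visit 2. With an assumed true risk of 10% and c down to 0.5, it reaches 5 points under the protocol's TEAE window and less under the SAP's. A reader might be tempted to quote a particular ratio, such as a doubling of AE rates; any such figure would only restate the value chosen for c.

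**What to change.** Reconcile protocol section 2 with section 4.6.

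- Use one identical, arm-neutral question in both arms at Visits 2 to 4, for example whether the child has had any health problem or discomfort since the last visit.
- If the DryNites question is kept, ask it after the open question, and add a solicited/unsolicited source field to the AE variables in section 7.2.
- Keep all AEs, however elicited, in the TEAE tables. Restricting those tables to events from the open question would drop known AEs for a device whose side-effects have not been studied.
- In SAP section 16.1, add a by-group presentation that leaves out events elicited only by the device prompt.

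The cost is one line in the visit script, one form field and one extra table.
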